3.4.3 Exploratory Endpoints

Change in carotid IMT by MR between Month 0 and Month 9.

4 STUDY POPULATION

4.1 Rationale for Subject Selection

Selection criteria for ECs were created based on the well-established definition that EC/Long-term Non-progressors are HIV-1 infected subjects with a suppressed viral load of <40 (or <48 or <50) copies/mL (depending on the assay used) in the absence of ART. Additionally, they have no history of opportunistic infections and stable CD4 T cells counts [83]. Selection criteria for Treated Progressors (ART <50) are based on the

accepted standard that HIV-1 infected individuals on ART who achieve virological suppression have a HIV-RNA level of <40 (or <48 or <50) copies/mL.

Since this study is seeking to establish the biomarker, cellular and cardiovascular effects of treatment with ATV and ASA, participants must not have received statin or ASA therapy for 6 months prior to the screening visit. In order to eliminate any confounding effects, patients will also be excluded if they have received any immunomodulating therapy, systemic corticosteroids or chronic daily nonsteroidal anti-inflammatory drugs (NSAID) use unless discussed with and approved by the study investigator.

4.2 Recruitment Plan

Subjects will be recruited from the NIH Clinical Center, particularly from the NIH CCMD/NIAID OP8 Clinic, and from University of Minnesota Hennepin County Medical Center. The study may also be advertised through web based campaign as study visits are infrequent and we may need to recruit from outside the local area.

Subjects recruited from University of Minnesota, Hennepin County will sign consents at this site and all screening procedures including initial history and physical Assessments, lab work to determine eligibility will be done before sending them to NIH clinical Center OP8 clinic. These subjects will continue into month 0 and complete the rest of the study visits at NIH.

Prior to study implementation, sites must obtain Institutional Review Board (IRB) approvals. Health care providers and research personnel at participating institutions will identify potentially eligible subjects. Once a subject for study entry is identified and expresses interest in learning about the study, the subject will be approached by the study team about participation in the protocol. If the subject remains interested, study details and the informed consent form (ICF) will be reviewed with the candidate by the study PI/designee. If the subject is willing to participate in the study, he or she will be provided with a copy of the informed consent to review. If a subject requires more time to consider the study, the staff member will give them a copy of the informed consent along with the staff member's contact information, so that subjects may take the documents home for further review. After questions related to the study and the informed consent has been answered to the subject's satisfaction, subjects will be asked to sign the IRB-approved consent form.

4.3 Subject Inclusion Criteria

EC Arm

1. Age \geq 18 years.
2. Documented HIV-1 infection confirmed by enzyme-linked immunosorbent assay (ELISA) and Western blot tests (will not be repeated if performed previously at NIH).
3. Categorized as a long term non-progressor EC as defined by viral loads typically less than the LLD of commercially available assays and clinical and laboratory criteria (no OIs, no ART, stable CD4 T cell counts for more than 3 years). Viral load "blips" are allowed as long as they are <500 copies/mL and flanked by viral

load measurements less than limit of detection of the commercially available assay. Viral load <100c/mL will be acceptable for eligibility at screening.

4. In women of childbearing potential, with no plans for pregnancy for the next 15 months and willing to use 2 investigator approved highly reliable methods of birth control consistently while on the study or in 3 month follow up.
5. Willingness to have samples stored for future research.
6. Not on a statin or ASA for the past 6 months.

ART <50 Arm

1. Age \geq 18 years.
2. Documented HIV-1 infection confirmed by enzyme-linked immunosorbent assay (ELISA) and Western blot tests.
3. In women of childbearing potential, with no plans for pregnancy for the next 15 months and willing to use 2 investigator approved highly reliable methods of birth control consistently while on the study or in 3 month follow up.
4. On continuous combination ART >4years.
5. HIV RNA <50 copies/mL (or <40 or <48 copies/mL, depending on the lower limit of detection of the assay used; transient periods of low level (<300) detectable virus, “blips,” acceptable if isolated and followed by <50 copies/mL values) >3 years and current HIV-RNA less than the LLD of the commercially available assay used. Subject will be rescreened if HIV detectable at screening visit.
6. Willingness to have samples stored for future research.
7. Not on a statin or ASA for the past 6 months.

4.4 Participation of Women:

Decreased cholesterol synthesis caused by ATV may cause fetal harm when administered to women who are pregnant; ATV has been listed as a pregnancy category X drug. ASA has been listed as a pregnancy category D drug by the Food and Drug Administration (FDA) due to the potential for known teratogenic or abortifacient effects on the developing fetus. Subjects must agree not to become pregnant. Females of childbearing potential must have a pregnancy test before initiating the study agent and at each study visit. Because of the risk involved, sexually active subjects and their partners must use 2 methods of birth control, one of which must be a barrier method. They must continue to use both methods until the end of study visit (Month 15). The methods of birth control may be selected from the list included below:

- Hormonal contraception
- Male or female condoms with or without a spermicide
- Diaphragm or cervical cap with a spermicide
- Intrauterine device (IUD)

- Male partner with a vasectomy

If pregnancy is suspected or should occur, subjects must notify the study staff immediately.

4.5 Subject Exclusion Criteria

1. Diagnosis of cardiovascular disease or hypercholesterolemia (LDL cholesterol \geq 190 mg/dL).
2. Known hypersensitivity or allergy to ATV or ASA, including a history of myositis or rhabdomyolysis with statin or ASA use.
3. Other contraindication for ASA or statin therapy (active liver disease, peptic ulcer disease, etc.).
4. Women who are lactating, pregnant, or actively trying to become pregnant or considering pregnancy over the likely span of the study (including women of childbearing potential who are unwilling to use adequate contraception throughout the study).
5. Any chronic inflammatory condition either requiring anti-inflammatory medication (systemic corticosteroids, daily NSAID use, immunomodulating medications) which may, in the opinion of the investigator, confound the interpretation of soluble inflammatory biomarkers. While on study, short term (less than 5 days) NSAID use will be allowed at the discretion of the investigator.
6. Active drug use or alcohol abuse that, in the opinion of the investigator, may interfere with the ability of the subject to participate in the study or that may unacceptably increase the risk of the study intervention.
7. Safety laboratory cut offs: coagulation (INR >2 upper limit of normal [ULN], PLT $<75K$), renal function (GFR <60), liver function (ALT or Alkaline phosphatase or direct bilirubin $>2x$ ULN), aldolase <1.5 ULN and anemia (Hb <9 mg/dL).
8. Antiretroviral therapy with tipranivir, or any therapy which combines non-nucleoside reverse transcriptase inhibitors with protease inhibitors.
9. Chronic hepatitis C co-infection. However, if a subject has more than 24 weeks of sustained virologic response (SVR), the subject can be considered for eligibility.
10. If either MR or apheresis is contraindicated, subject may still participate without this procedure. In the case of missed apheresis, a 30 mL research blood draw will be substituted (see Appendices B and C).
11. If statin initiation is indicated per current guidelines, subject will be counseled to consult with their PMD. If the subject then chooses to take part in the study, we will provide their PMD with all pertinent lab results during the course of the study, if requested.

Co-enrollment Guidelines: Co-enrollment in other trials will be restricted, other than enrollment on observational studies. Study staff should be notified of co-enrollment as it may require the approval of the Investigator.

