5.7 Prohibited Medications and Procedures

Treatment with immunomodulating agents, systemic corticosteroids and daily NSAIDs will not be permitted unless discussed with and approved by the study investigator. Subjects treated with a statin or ASA daily up to 6 months prior to the screening visit will also be excluded. Treatment with tipranavir will be prohibited because ATV is contraindicated in these patients. Treatment with any ART regimen combining a non-nucleoside reverse transcriptase inhibitor with a protease inhibitor will be prohibited because of the lack of data concerning drug interactions with ATV.

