Hepatic Insufficiency: Avoid aspirin in patients with severe hepatic insufficiency.

Sodium Restricted Diets: Patients with sodium-retaining states, such as congestive heart failure or renal failure, should avoid sodium-containing buffered aspirin preparations because of their high sodium content.

Laboratory Tests

Aspirin has been associated with elevated hepatic enzymes, blood urea nitrogen and serum creatinine, hyperkalemia, proteinuria, and prolonged bleeding time.

Drug Interactions

Angiotensin Converting Enzyme (ACE) Inhibitors: The hyponatremic and hypotensive effects of ACE inhibitors may be diminished by the concomitant administration of aspirin due to its indirect effect on the renin-angiotensin conversion pathway.

Acetazolamide: Concurrent use of aspirin and acetazolamide can lead to high serum concentrations of acetazolamide (and toxicity) due to competition at the renal tubule for secretion.

Anticoagulant Therapy (Heparin and Warfarin): Patients on anticoagulation therapy are at increased risk for bleeding because of drug-drug interactions and the effect on platelets. Aspirin can displace warfarin from protein binding sites, leading to prolongation of both the prothrombin time and the bleeding time. Aspirin can increase the anticoagulant activity of heparin, increasing bleeding risk.

Anticonvulsants: Salicylate can displace protein-bound phenytoin and valproic acid, leading to decrease in the total concentration of phenytoin and an increase in serum valproic acid levels.

Beta Blockers: The hypotensive effects of beta blockers may be diminished by the concomitant administration of aspirin due to inhibition of renal prostaglandins, leading to decreased renal blood flow, and salt and fluid retention.

Diuretics: The effectiveness of diuretics in patients with underlying renal or cardiovascular disease may be diminished by the concomitant administration of aspirin due to inhibition of renal prostaglandins, leading to decreased renal blood flow, and salt and fluid retention.

Methotrexate: Salicylate can inhibit renal clearance of methotrexate, leading to bone marrow toxicity, especially in the elderly or renal impaired.

Nonsteroidal Anti-inflammatory Drugs (NSAIDs): The concurrent use of aspirin with other NSAIDs should be avoided because this may increase bleeding or lead to decreased renal function.

Oral Hypoglycemics: Moderate doses of aspirin may increase the effectiveness of oral hypoglycemic drugs, leading to hypoglycemia.

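### Short NSAID courses are allowed on study although the appended aspirin label says to avoid them with aspirin, and nothing separates or reliably records such use around research draws

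*Combined protocol and SAP*

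**What the plan says.** **NSAIDs.** Section 4.5 item 5 excludes chronic inflammatory conditions whose treatment could confound the soluble markers, then adds: "While on study, short term (less than 5 days) NSAID use will be allowed at the discretion of the investigator". It draws no distinction by arm and sets no limit on the number of courses. The other NSAID passages concern daily use. Section 5.7 states: "Treatment with immunomodulating agents, systemic corticosteroids and daily NSAIDs will not be permitted unless discussed with and approved by the study investigator". Section 5.3.2 leaves the prohibition of daily use to the principal investigator's discretion. Section 11.10 makes a condition that needs daily NSAIDs a reason to stop study drug.

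**Aspirin label.** Appendix E, under Drug Interactions, says: "The concurrent use of aspirin with other NSAIDs should be avoided because this may increase bleeding or lead to decreased renal function". On heparin and warfarin it says: "Patients on anticoagulation therapy are at increased risk for bleeding because of drug-drug interactions and the effect on platelets". Section 8.1 summarises the label's warnings (alcohol, coagulation, gastrointestinal, ulcer, renal, hepatic, sodium) but none of its drug interactions.

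**Anticoagulants.** Sections 4.5, 5.3.2, 5.7, 8.1 and 11.10 do not name them. The nearest entry criteria, all in section 4.5, are item 1 ("Diagnosis of cardiovascular disease or hypercholesterolemia"), item 3 ("Other contraindication for ASA or statin therapy (active liver disease, peptic ulcer disease, etc") and item 7 ("INR >2 upper limit of normal").

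**Recording and sampling.** Section 5.6 documents all prescription drugs in the database. Its wording on over-the-counter drugs can be read as limited to those taken around adverse events above grade 1. Sections 6.4 to 6.7 take an over-the-counter history at Months 3 to 15. Section 6 gives every visit after baseline a window of ±2 weeks.

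**The concern.** Randomisation is 1:1, so half of the planned 80 participants take aspirin. For them, section 4.5 item 5 permits something that the protocol's own appendix says to avoid, and no passage in the body alerts the investigator to this. The antiretroviral interactions of atorvastatin, by contrast, are carried into section 4.5 item 8, section 5.3.1 with Table 1, and section 5.7.

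There is also a measurement question. Sections 4.1 and 4.5 treat anti-inflammatory drugs as potential confounders of the markers under study. A short course that overlaps a research draw could affect hsCRP or IL-6, which are secondary endpoints in section 3.4.2. The within-arm paired tests in section 13.5 have no untreated arm against which such an effect would cancel. If the use is not in the database, it cannot be examined afterwards.

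**Working it through.** **1. The NSAID passages side by side.**
- Section 4.5 item 5: courses under 5 days allowed, both arms, investigator's discretion.
- Sections 5.3.2, 5.7 and 11.10: daily use only; nothing on short courses.
- Section 8.1: aspirin–NSAID interaction absent.
- Appendix E: avoid the combination; no short-course exemption.

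The first and last entries conflict for aspirin participants, and nothing between them resolves it.

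**2. Recording.** The qualifier about adverse events in section 5.6 may attach to over-the-counter drugs or only to the last item in its list. On the first reading, over-the-counter NSAID use without an adverse event of grade 2 or above appears in the visit history but not in the database.

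**3. Anticoagulants.** Item 7 can mean INR above 2 or INR above twice the upper limit of normal. The documents give no upper limit. If it is assumed to be 1.1 to 1.2, the second reading puts the cut-off at 2 × 1.1 = 2.2 to 2 × 1.2 = 2.4. On either reading, a participant on an anticoagulant whose INR stays below the limit passes item 7. Item 3 is open-ended, but Appendix E places anticoagulants under Precautions, not Contraindications, so whether item 3 covers them is left to the reader.

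**4. Primary endpoint: the plan's own figure.** Inputs from section 13.2: SD 0.45 µg/mL, correlation 0.71, difference 0.20 µg/mL, 40 per arm, two-sided 0.05, paired t test.
- SD of the paired difference = 0.45 × √(2 × (1 − 0.71)) = 0.343.
- Power from the noncentral t distribution = 94.9%, which reproduces the stated 95%.

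**5. Primary endpoint: an assumption-only range.** Suppose a share f of an arm is under NSAID influence at Month 12 only, and that this lowers sCD14 by s. Both values are assumed; the documents give neither.
- Bias in mean change = f × s.
- SD of the difference = √(0.343² + f(1 − f)s²).

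| f | s (µg/mL) | Bias (µg/mL) | Share of 0.20 | Power at a true 0.20, added variance only | Chance of significance with no drug effect |
|---|---|---|---|---|---|
| 5% | 0.05 | 0.0025 | 1.25% | 94.9% | 5.0% |
| 10% | 0.10 | 0.010 | 5% | 94.8% | 5.4% |
| 10% | 0.20 | 0.020 | 10% | 94.3% | 6.5% |
| 20% | 0.20 | 0.040 | 20% | 93.9% | 10.8% |

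The disturbance is small except in the last row, where one participant in five shifts by the whole target difference. The same calculation cannot be done for hsCRP, IL-6 or the coagulation markers, because the plan gives no SDs for them.

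**6. Feasibility.** The visit window spans 28 days and a permitted course lasts fewer than 5, so a Month 3 or Month 12 draw can be moved clear of the days of an NSAID course without changing the schedule.

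**The case against.** The strongest reply is that the protocol leaves short NSAID use to the investigator. In an open-label trial the investigator knows who takes aspirin and can apply the label case by case. The label statement is a precaution, not a contraindication, and daily NSAIDs are already restricted. This softens the safety conflict, but the two texts still disagree. It also has a statistical cost: if discretion is exercised differently by arm, NSAID use differs by arm, which is the condition under which the aspirin–atorvastatin comparison would be biased.

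On anticoagulants, the reply largely succeeds. A reader might infer that the protocol has no protection at all. In fact section 4.5 items 1, 3 and 7 give partial cover at entry. Section 11.10 has a general best-interest stopping rule and lets a newly developed exclusion criterion count as cause to stop. PT/PTT is measured at every visit, and section 5.6 records prescription drugs. Moreover, the endpoints are mainly within-person changes, so stable anticoagulation at both draws would affect level more than change. Only starting or stopping between draws clearly matters.

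It is also fair to say that the documents report no marker effect of a short NSAID course. The confounding argument rests on the protocol's own caution about anti-inflammatory drugs, not on data.

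**Conclusion.** The NSAID conflict is in the text and needs to be reconciled. Aspirin participants may be exposed to a combination that the appended label cautions against. Inflammation markers may be confounded, because use is neither separated from draws nor clearly captured in the database. The anticoagulant part is a lesser matter: an omission by name with partial indirect cover, plus an ambiguous INR limit.

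Three stronger readings are tempting and are not supported:
- **That participants are in fact exposed and markers in fact disturbed.** No passage gives a rate of NSAID or anticoagulant use, or an effect of either on a marker.
- **That the INR criterion admits values up to 2.2 to 2.4.** This needs one of two readings and an upper limit of normal that the documents do not state.
- **That the primary result is compromised.** No effect on sCD14 is shown. Under the assumed ranges (f 5% to 20%, s 0.05 to 0.20 µg/mL, Month 12 only), bias is 0.0025 to 0.04 µg/mL against a target of 0.20, and power stays at 93.9% or above.

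**What to change.** - Reconcile section 4.5 items 5 and 7 and sections 5.3.2, 5.7, 8.1 and 11.10 with the interactions in Appendix E, including what applies to anticoagulants. The clinical rule is for the investigators to set.
- State which meaning of the INR limit in item 7 is intended.
- Enter any NSAID use, including over-the-counter, in the database before each research draw, whether or not there is an adverse event.
- When an NSAID course is under way at a scheduled post-baseline draw, move the draw within the existing ±2-week window.
- If any participant starts or stops an anticoagulant between draws, repeat the coagulation-marker analyses without that participant. If none does, no extra analysis is needed.

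The cost is minor protocol wording, a small amount of data entry at each visit, and occasional rescheduling inside a window that already exists. Sample size and visit schedule are unchanged.

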11.10 Stopping Rules for an Individual Subject/Cohort

A study subject will be discontinued from further Study Agent(s)/Intervention(s) administration for:

- Any clinical AE, laboratory abnormality, intercurrent illness, other medical condition or situation occurs such that continued participation in the study would not be in the best interest of the subject.
- Development of any exclusion criteria may be cause for discontinuation.
- Grade 3 or 4 adverse reactions to the study drug, including myalgia, abdominal pain, and nausea.
- Grade 3 elevation of hepatic transaminases that is confirmed by repeated testing and is considered related to study drug.
- New pregnancy (see Section [6.9](#)).
- Development of allergy or hypersensitivity to study drug.
- Request by participant to withdraw from study.
- Development of a medical condition that requires administration of the following prohibited concomittent medications:
 - Systemic corticosteroids
 - Daily NSAIDs

- Immunomodulating medication
- Subject is judged to be at risk of failing to adhere to the study provisions to such a degree that, in the opinion of the investigator, the integrity of the study results might become compromised.

For all subjects withdrawn from study, the PI will evaluate on an individual basis if it is in the best interest of the participant to be followed by the protocol team with follow-up visits that include safety laboratory tests.

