APPENDIX B: SCHEDULE OF PROCEDURES/EVALUATIONS

(After baseline, all visit windows \pm 2 weeks)

Evaluation	Screening (0 days– 2 months)	Baseline (Month 0)	Month 3	Month 6	Month 9	Month 12	Month 15
Medical/Medication History	X	X	X	X	X	X	X
Clinical Assessment	X	X	X	X	X	X	X
Physical Exam ¹	X	X	X	X	X	X	X
Carotid MRI ²		X				X	
Rectal swab & dietary questionnaire		X				X (swab only)	
Apheresis (2-Pass) ³			X			X	
CBC, differential, platelets	X	X	X	X	X	X	X
PT/PTT/D-dimer	X	X	X	X	X	X	X
Acute Care/Hepatic Panel/Mineral Panel/hsCRP/CK/Aldolase	X	X	X	X	X	X	X
Urinalysis	X	X	X	X	X	X	X
Pregnancy Testing	X	X	X	X	X	X	X
CD4/HIV-1 RNA	X	X	X	X	X	X	X
Hemoglobin A1c		X	X	X	X	X	X
Lipid Panel (fasting)	X	X	X	X	X	X	X
Hepatitis Serology	X						
ELISA/Western Blot	X ⁴						
Research Storage (Plasma, PBMC, Serum)		X	X	X	X	X	X
Research Flow Cytometry		X	X	X	X	X	X
Atorvastatin or Aspirin Dispensed			X	X	X		
Pill Count			X	X	X	X	

¹ Targeted physical exam for acute presentations following screening visit.

² Can occur any time on or between the M0 and M3 visits, based on MR availability.

³ If adequate venous access and Hg>9g/dL and PLT>50,000. If inadequate venous access, 30mL of additional blood will be drawn in lieu of apheresis (3-10mL green tops)

⁴ If not previously performed at NIH

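### Exclusion criterion 7 has a reversed aldolase limit and a haemoglobin limit in the wrong unit, so neither works as written

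*Combined protocol and SAP*

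**What the plan says.** Section 4.5, item 7 is a list of laboratory results that bar entry. It opens with coagulation and renal limits: "Safety laboratory cut offs: coagulation (INR >2 upper limit of normal [ULN], PLT $<75K$), renal function (GFR <60". It continues with "liver function (ALT or Alkaline phosphatase or direct bilirubin $>2x$ ULN" and closes with "aldolase <1.5 ULN and anemia (Hb <9 mg/dL".

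Three other places bear on these limits:

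- Section 11.10, on stopping an individual subject: "Development of any exclusion criteria may be cause for discontinuation".
- Appendix B, footnote 3, on who may undergo apheresis: "If adequate venous access and Hg>9g/dL and PLT>50,000".
- Appendix B, laboratory row: "Acute Care/Hepatic Panel/Mineral Panel/hsCRP/CK/Aldolase" is marked at screening and at every later visit, as is the blood count.

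Neither exclusion limit is restated or corrected anywhere else in the document.

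**The concern.** An exclusion list should name the abnormal side of each test. The aldolase entry names the normal side, and the haemoglobin entry uses a unit that makes it empty.

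Aldolase is the only muscle enzyme with a numeric limit in item 7. Creatine kinase is drawn at every visit but has no cut-off in item 7 or in Section 11.10. The protocol warns in Section 8.1 of myopathy and rhabdomyolysis, with more risk alongside HIV protease inhibitors, and Section 5.3.1 allows atorvastatin doses up to 80 mg. As printed, the one numeric muscle-enzyme gate works backwards.

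Item 7 also holds the only numeric haemoglobin limit on entry. It applies before possible randomisation to aspirin, for which Section 8.1 lists gastrointestinal bleeding, and before blood draws of 114.5 to 146.5 mL per visit from Month 0 (Appendix C). As printed, it does nothing.

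Because Section 11.10 points back to the exclusion criteria, both errors also reach the treatment period. There is an audit problem too: Section 11.4 counts any departure from approved procedures as a protocol deviation, so, read literally, enrolling anyone with a normal aldolase is a deviation.

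**Working it through.** The plan gives no derived figure to reproduce here. The check has three steps: the direction of each limit, a unit conversion, and each printed rule applied to a range of values.

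**1. Direction of the limits in item 7 set against the ULN**

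| Test | Excludes if | Side excluded |
|---|---|---|
| INR | >2 ULN | high |
| ALT | >2x ULN | high |
| Alkaline phosphatase | >2x ULN | high |
| Direct bilirubin | >2x ULN | high |
| Aldolase | <1.5 ULN | low |

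Four of the five exclude high values and one excludes low values. The remaining limits in the item (platelets <75K, GFR <60) also name the abnormal side, which for those tests is low.

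**2. Aldolase rule applied**

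A normal result is by definition at most 1.0 x ULN. Since 1.0 < 1.5, every normal result meets the printed exclusion. No assumption about the population is needed.

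| Aldolase (x ULN) | Excluded as printed (<1.5) | Excluded if corrected (>1.5) |
|---|---|---|
| 0.1 | yes | no |
| 0.5 | yes | no |
| 1.0 | yes | no |
| 1.49 | yes | no |
| 1.5 | no | no |
| 2 | no | yes |
| 3 | no | yes |

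**3. Haemoglobin rule applied**

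Conversion: 9 mg/dL ÷ 1000 = 0.009 g/dL. Ratio to the value in Appendix B, footnote 3: 9 g/dL ÷ 0.009 g/dL = 1000.

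| Hb (g/dL) | In mg/dL | Excluded as printed (<9 mg/dL) | Excluded if corrected (<9 g/dL) |
|---|---|---|---|
| 5 | 5000 | no | yes |
| 7 | 7000 | no | yes |
| 8.9 | 8900 | no | yes |
| 9 | 9000 | no | no |
| 12 | 12000 | no | no |
| 15 | 15000 | no | no |

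**4. Data available to apply corrected limits**

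Appendix B marks both the aldolase row and the blood-count row at screening and Months 0, 3, 6, 9, 12 and 15: 1 + 6 = 7 time points.

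**The case against.** The strongest reply is that both errors correct themselves on reading. A literal aldolase rule would turn away everyone with a normal result, so staff are very unlikely to apply it. The haemoglobin limit carries the label anemia, and its unit is physically impossible. Other protections remain: items 2 and 3 of Section 4.5, creatine kinase and aldolase at every visit, the separate haemoglobin gate for apheresis, stopping for grade 3 or 4 reactions including myalgia, and staff review of results as they arrive (Section 12.1). Section 11.10 is permissive where it cites the exclusion criteria, and its first bullet already lets the investigator act on any laboratory abnormality when continuing is not in the subject's interest. A raised aldolase or a haemoglobin of 8 g/dL on treatment could therefore still be acted on. All of this stands and limits the practical effect.

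A second reply is that the aldolase point rests on a single character in text extracted from a PDF. Section 8.1 shows a similar flip: it gives persistent transaminase elevations as below 3 times ULN, where the package insert in Appendix D (its section 5.2) has above 3 times. That could come from the authors or from the extraction, and the text does not settle which. An extraction error therefore cannot be fully ruled out for aldolase, although the other signs in item 7 read sensibly. It would not explain the haemoglobin unit.

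A third reply is that footnote 3 governs apheresis and not entry, and that its platelet limit (50,000) differs from item 7's (75K). That is correct. The footnote supports the unit but does not restate the exclusion threshold, which is why the investigators should confirm the value.

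**Conclusion.** The concern holds. As written, the aldolase limit excludes every normal result and admits only values at or above 1.5 ULN, and the haemoglobin limit excludes no one. The first follows from the definition of the upper limit of normal and the second from a unit conversion. The only assumption is that the printed less-than sign for aldolase is the authors' own; the haemoglobin finding does not depend on it.

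The consequence is modest. The intended limits can be inferred, other safeguards cover much of the risk, nothing in the documents shows wrong enrolment, and sample size, power and analysis are unaffected. The correction is still worth making, because staff should not have to override approved wording to screen safely, and eligibility cannot be audited against the present text.

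**What to change.** Amend Section 4.5, item 7 to exclude aldolase >1.5x ULN and Hb <9 g/dL, with the investigators confirming that both are the thresholds they intend. Section 11.10 needs no separate edit, since it refers back to the exclusion criteria and is corrected with them.

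Compare the screening aldolase and haemoglobin of participants already enrolled with the corrected limits. This does not presume that anyone was wrongly admitted; it puts the eligibility record on a sound footing.

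The cost is a one-line protocol amendment and a check of results already held. No procedure or blood draw is added, because both tests are already scheduled at screening and every visit.
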